Since patients who discontinue the treatment with the IMP will not be withdrawn from the study but will be asked to complete safety and efficacy assessments as per the protocol, missing data under treatment policy strategy will be addressed by modeling patients with missing data after retrieved drop-outs (based on assumption of missing data would have been like retrieved drop-outs if they were assessed). Retrieved drop-out patients are defined as patients who discontinue study treatment and decide to remain in the study by following the schedule of assessments and continuing to adhere to protocol requirements.

If enough retrieved drop-out data are available to allow convergence of a regression model, a Multiple Imputation model based on retrieved drop-outs (MI-RD) will be used for analysis. Specifically, MI will be performed based on the subjects' allocated treatment arm and observed values (baseline and intermediate) as covariates in a regression model using data from subjects that discontinued the treatment but have the primary endpoint measurement with gender, and age class as covariates. For each co-primary endpoint, MI-RD will be implemented into different steps:

- Intermittent missing data up to primary time point (Week 4 for Schirmer I test, and Week 12 for SANDE) will be imputed using MCMC methods assuming missing at random (MAR) data;
- The remaining missing values with a monotone missing data pattern will be imputed based on observed data of retrieve dropouts;

- the fully imputed datasets will be analyzed and results will be combined using Rubin's to draw inference.

If not enough data was retrieved after study treatment discontinuation for assure the convergence of the MI-RD regression model (the final decision will be done at the time of the analysis and reported in the CSR; different approaches might be used for the two coprimary endpoint), the same model will be fit using data from subjects of control group, washing-out the effect of treatment; this approach does not assume benefits for cenegermin in case of discontinuation and limits a post-discontinuation clinical effect to that of vehicle. Specifically, wash-out approach will be implemented in this way:

- Intermittent missing data up to primary time point (Week 4 for Schirmer I test, and Week 12 for SANDE) will be imputed using MCMC methods assuming MAR;

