ANCOVA	Analysis of Covariance
ATC	Anatomical Therapeutic Chemical
BCDVA	Best Corrected Distance Visual Acuity
BDRM	Blind Data Review Meeting
CSR	Clinical Study Report
eCRF	electronic Case Report Form
ENR	Enrolled set
EU	European Union
FAS	Full Analysis set
KFR	Key First efficacy Results
IDEEL	Impact of dry eye on everyday life
IMP	Investigational Medicinal Product
MAR	Missing at Random
MCMC	Markov chain Monte Carlo
MedDRA	Medical Dictionary for regulatory activities
MI	Multiple Imputation
MI-RD	Multiple Imputation using retrieve dropouts
MMRM	Mixed Model for Repeated Measurements
MNAR	Missing Not at Random
NEI	National Eye Institute
PP	Per protocol set
PT	Preferred Term
rhNGF	recombinant human Nerve Growth Factor
RND	Randomized set
SAE	Serious Adverse Event
SAF	Safety set
SANDE	Symptom Assessment in Dry Eye
SAP	Statistical Analysis Plan
SEM	Standard error of the mean
SOC	System Organ Class
TEAE	Treatment Emergent Adverse Event
TFBUT	Tear Film Break-Up Time
TID	Ter in die (three times a day)
US	United States

1. Revision History

Table 1: Revision history

Document Version	Changes Made	Document Date
Final 1.0	First release.	CCI [REDACTED]
Final 2.0	Alignment with study protocol Version No. 6.0 – 26 January 2022. Clarifications added in section 7.9, 7.10, 9.2, 9.3, 10.2, and 11.1. Clarifications and new subgroup analysis added in section 7.5. TFL appendices in section 15. SAS code for primary analysis in appendix. Editorial corrections.	CCI [REDACTED]
Final 3.0	The overview of planned statistical analyses (section 6.2) has been updated. Clarifications added in section 10.1.1.	CCI [REDACTED]

2. Introduction

This document outlines the statistical methods to be implemented in the analysis of the data of NGF0121 Clinical Trial. The purpose of this plan is to provide general guidelines from which the analysis will proceed, containing a more technical and detailed elaboration of the principal features of the analysis described in the protocol. Any changes to the protocol or Case Report Form (CRF) may necessitate updates to the Statistical Analysis Plan (SAP). In case of deviations from this updated SAP, explanations will be provided in the Clinical Study Report (CSR).

This SAP is based on study protocol Version **CCI**

3. Study Design

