7.9 Changes in the planned analysis

The following changes have been included, compared to the protocol [1]:

- In the secondary endpoint on SANDE, the global score has been included (section 3.2.2) in addition to severity and frequency scores.
- In the explorative endpoint on SANDE, the global score has been included (section 3.2.3) in addition to severity and frequency scores.
- A clarification on the use of data from blinded reading center and site investigator has been added in section 7.8.
- The first key secondary endpoint in section 10.2.1 has been reworded in alignment with the definition of the Schirmer I test primary endpoint.
- A clarification on the use of a Mixed Model for Repeated Measurements (MMRM), extension of ANCOVA for repeated measurements, after imputation through MI-RD for IDEEL, NEI scale and TFBUT endpoints has been added in section 10.2.2, in alignment with treatment policy estimand used for primary endpoint.
- Considering the progress of data collection, the overview of planned statistical analyses (section 6.2) has been updated. A single database lock will be performed at the end of the study (instead of two locks), followed by the release of the KFR and by the final analyses. This decision represents a conservative choice in favor of the integrity of the study.

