10.1.2 Analysis details

Both co-primary endpoints will be analysed by means of MI-RD to handle missing data. Retrieved drop-out patients are defined as patients who discontinue study treatment and decide to remain in the study by following the schedule of assessments and continuing to adhere to protocol requirements. Consequently, for each primary endpoint, MI will be performed based on the subjects' allocated treatment arm and observed values (baseline and intermediate) as covariates in a regression model using data from Retrieved drop-out patients that have the primary endpoint assessment done.

10.1.2.1 Schirmer I test $>10\text{mm}/5\text{min}$ at week 4

This primary endpoint will be analyzed by means of a logistic regression model adjusting by pre-defined baseline factors (gender, age class, baseline Schirmer I test value as fixed effects and site as random effect) and a one-sided test will be used to test for differences between treatment groups.

For the imputation of missing data of Schirmer I test, a regression model will be created by including the baseline Schirmer I test value, gender, age class, and Schirmer I test at week 2. Two hundred data sets will be generated, and the random seed number will be 820520. MI will be implemented in the following steps:

1. Partial imputation assuming Missing at Random (MAR) will be carried out to impute intermittent (non-monotone) missing data of Schirmer I test up to week 4 based on a

multivariate joint Gaussian imputation model using the Markov chain Monte Carlo (MCMC) method. A separate imputation model will be used for each treatment arm. In case of non-convergence or non-estimability issues, a single imputation model will be considered (with treatment arm added as explanatory variable to the model). A total of 200 datasets will be created. These datasets will be utilized in Step #2.

2. The remaining monotone missing data will be imputed using a MI regression including the same explanatory variables of the previous step. According to MI-RD approach, only non-missing values from retrieve dropouts will be used to inform the regression model.
3. Each of the 200 imputed datasets will be analyzed using observed and imputed data. Rubin's rule will be used for combining results to draw inference.

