If there are not enough retrieved dropouts for convergence of MI-RD regression model, a reference-based Multiple Imputation (MI) approach will be adopted to consider a missing not at random (MNAR) mechanism for missing data: imputation of values in the rhNGF arm (above step #2) will be done using the non-missing values from the control group (this approach will be referred as "Copy Reference"). This approach does not assume benefits for rhNGF in case of discontinuation and limits a post-discontinuation clinical effect to that of vehicle. The final decision on the use of the MI-RD vs Copy-Reference for this endpoint will be done at the time of the analysis and reported in the CSR.

Whether for MI-RD or Copy-Reference approach, the adjusted estimated treatment differences in proportions between cenegegermin and vehicle at week 4 will be displayed together with the corresponding two-side 95% confidence intervals and p-value.

10.1.2.2 Change from baseline in the global SANDE score at week 12

This co-primary endpoint will be analyzed by means of an Analysis of Covariance (ANCOVA) adjusting by pre-defined baseline factors (gender, age class, baseline global SANDE score as fixed effects and site as random effect) and a one-sided test will be used to test for differences between treatment groups. Rules for derivation of SANDE scores are reported in section 12.2.

For the imputation of missing data, a regression model will be created by including the baseline global SANDE score, gender, age class, and intermediate global SANDE scores up to week 12. Two hundred data sets will be generated, and the random seed number will be 37103939. MI will be implemented in the following steps:

1. Partial imputation assuming MAR will be carried out to impute intermittent (non-monotone) missing data of global SANDE score based on a multivariate joint Gaussian imputation model using the MCMC method. A separate imputation model will be used for each treatment arm. In case of non-convergence or non-estimability issues, a single imputation model will be considered (with treatment arm added as explanatory variable to the model). A total of 200 datasets will be created. These datasets will be utilized in Step #2.
2. The remaining monotone missing data will be imputed using a MI regression including the same explanatory variables of the previous step. According to MI-RD approach, only non-missing values from retrieve dropouts will be used to inform the regression model.

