15.5 SAS Code for the primary analysis

15.5.1 Schirmer I test >10mm/5min at week 4

Standard	Alternative code in case of no convergence
<pre> PROC MI DATA= EFFICACY01 NIMPUTE=200 SEED=820520 OUT=EFFICACY_MONO1; VAR BASVAL SCHIRMER_W2 AVAL; MCMC CHAIN=SINGLE NBITER=200 NITER=100 IMPUTE=MONOTONE; WHERE TRT=1; RUN; PROC MI DATA=EFFICACY01 NIMPUTE=200 SEED=820520 OUT=EFFICACY_MONO2; VAR BASVAL SCHIRMER_W2 AVAL; MCMC CHAIN=SINGLE NBITER=200 NITER=100 IMPUTE=MONOTONE; WHERE TRT=2; RUN; DATA EFFICACY_MONO; SET EFFICACY_MONO1 EFFICACY_MONO2; RUN; </pre>	<pre> PROC MI DATA= EFFICACY01 NIMPUTE=200 SEED=820520 OUT=EFFICACY_MONO; VAR BASVAL TRT SCHIRMER_W2 AVAL; MCMC CHAIN=SINGLE NBITER=200 NITER=100 IMPUTE=MONOTONE; RUN; </pre>
<pre> PROC SORT; BY _IMPUTATION_ SUBJID; RUN; </pre>	
<pre> PROC MI DATA=EFFICACY_MONO SEED=200582 NIMPUTE=1 OUT=EFFICACY_IMP; BY _IMPUTATION_; CLASS TRT AGE SEX EOTSTT; MONOTONE REG(AVAL = TRT AGE SEX BASVAL / DETAILS); MNAR MODEL(AVAL / MODELOBS= (EOTSTT='NOT COMPLETED')); VAR TRT AGE SEX BASVAL SCHIRMER_W2 AVAL; RUN; </pre>	<pre> PROC MI DATA=EFFICACY_MONO SEED=200582 NIMPUTE=1 OUT=EFFICACY_IMP; BY _IMPUTATION_; CLASS TRT AGE SEX EOTSTT; MONOTONE REG(AVAL = TRT AGE SEX BASVAL / DETAILS); MNAR MODEL(AVAL / MODELOBS= (TRT=2 /*Vehicle*/)); VAR TRT AGE SEX BASVAL SCHIRMER_W2 AVAL; RUN; </pre>

Standard	Alternative code in case of no convergence
<pre> DATA EFFICACY_IMP; SET EFFICACY_IMP; IF AVAL>10 THEN AVALC='Y'; ELSE AVALC='N'; RUN; ODS OUTPUT DIFFS=GLIMMIX_DIFFS; ODS OUTPUT PARAMETERESTIMATES=ESTIMATES; PROC GLIMMIX DATA=EFFICACY_IMP METHOD = QUAD; BY _IMPUTATION_; CLASS TRT(REF="1") AGE(REF="<=XX") SEX(REF="F") SITEID; MODEL AVALC(EVENT='Y')=TRT AGE SEX BASVAL /S DIST=BINARY LINK=LOGIT OR; RANDOM INTERCEPT / SUBJECT=SITEID; LSMEANS TRT / ILINK ODDSRATIO CL DIFF; RUN; ODS OUTPUT PARAMETERESTIMATES=POOLED_ESTIMATES; PROC MIANALYZE PARMS = ESTIMATES ; CLASS TRT AGE SEX; MODELEFFECTS INTERCEPT TRT AGE SEX BASVAL ; RUN; ODS OUTPUT PARAMETERESTIMATES=POOLED_DIFFS; PROC MIANALYZE DATA = GLIMMIX_DIFFS ; MODELEFFECTS ESTIMATE; STDERR STDERR; RUN; DATA POOLED_ODDS_RATIO; SET POOLED_DIFFS; ODDSRATIO=EXP(ESTIMATE); ODDS_95LL=EXP(LCLMEAN); ODDS_95UL=EXP(UCLMEAN); RUN; </pre>	

15.5.2 Change from baseline in the global SANDE score at week 12

Standard	Alternative code in case of no convergence

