<pre> PROC MI DATA= EFFICACY01 NIMPUTE=200 SEED=37103939 OUT=EFFICACY_MONO1; VAR BASVAL SANDE_W2 SANDE_W4 SANDE_W8 AVAL; MCMC CHAIN=SINGLE NBITER=200 NITER=100 IMPUTE=MONOTONE; WHERE TRT=1; RUN; PROC MI DATA=EFFICACY01 NIMPUTE=200 SEED=37103939 OUT=EFFICACY_MONO2; VAR BASVAL SANDE_W2 SANDE_W4 SANDE_W8 AVAL; MCMC CHAIN=SINGLE NBITER=200 NITER=100 IMPUTE=MONOTONE; WHERE TRT=2; RUN; DATA EFFICACY_MONO; SET EFFICACY_MONO1 EFFICACY_MONO2; RUN; </pre>	<pre> PROC MI DATA= EFFICACY01 NIMPUTE=200 SEED=37103939 OUT=EFFICACY_MONO; VAR BASVAL TRT SANDE_W2 SANDE_W4 SANDE_W8 AVAL; MCMC CHAIN=SINGLE NBITER=200 NITER=100 IMPUTE=MONOTONE; RUN; </pre>
<pre> PROC SORT; BY _IMPUTATION_ SUBJID; RUN; </pre>	
<pre> PROC MI DATA=EFFICACY_MONO SEED=200582 NIMPUTE=1 OUT=EFFICACY_IMP; BY _IMPUTATION_; CLASS TRT AGE SEX EOTSTT; MONOTONE REG(AVAL = TRT AGE SEX / DETAILS); MNAR MODEL(AVAL / MODELOBS= (EOTSTT='NOT COMPLETED')); VAR TRT AGE SEX BASVAL SANDE_W2 SANDE_W4 SANDE_W8 AVAL; RUN; </pre>	<pre> PROC MI DATA=EFFICACY_MONO SEED=200582 NIMPUTE=1 OUT=EFFICACY_IMP; BY _IMPUTATION_; CLASS TRT AGE SEX EOTSTT; MONOTONE REG(AVAL = TRT AGE SEX / DETAILS); MNAR MODEL(AVAL / MODELOBS= (TRT=2 /*Vehicle*/)); VAR TRT AGE SEX BASVAL SANDE_W2 SANDE_W4 SANDE_W8 AVAL; RUN; </pre>

Standard	Alternative code in case of no convergence
<pre>ODS OUTPUT DIFFS=DIFFS; ODS OUTPUT PARAMETERESTIMATES=ESTIMATES; PROC MIXED DATA=EFFICACY_IMP; BY _IMPUTATION_; CLASS TRT(REF="1") SEXC(REF="F") SITEID; MODEL AVAL=TRT AGE SEXC BASVAL /S; RANDOM INTERCEPT / SUBJECT=SITEID; LSMEANS TRT / CL DIFF; RUN; ODS OUTPUT PARAMETERESTIMATES=POOLED_ESTIMATES; PROC MIANALYZE PARMS = ESTIMATES ; CLASS TRT SEXC; MODELEFFECTS INTERCEPT TRT AGE SEXC BASVAL ; RUN; ODS OUTPUT PARAMETERESTIMATES=POOLED_DIFFS; PROC MIANALYZE DATA = DIFFS ; MODELEFFECTS ESTIMATE; STDERR STDERR; RUN;</pre>

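### The printed step 2 imputation code for both co-primary endpoints omits baseline and earlier SANDE scores and week-2 Schirmer, which the SAP text and protocol require

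*SAP*

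**What the plan says.** **Text.** SAP 10.1.2.2 defines the SANDE imputation model as "including the baseline global SANDE score, gender, age class, and intermediate global SANDE scores up to week 12". SAP 10.1.2.1 defines the Schirmer model as "including the baseline Schirmer I test value, gender, age class, and Schirmer I test at week 2". The opening paragraph of 10.1.2 adds allocated arm. For step 2 both subsections say: "The remaining monotone missing data will be imputed using a MI regression including the same explanatory variables of the previous step". Protocol 9.4.3.1 likewise calls for arm, gender, age class and "observed values (baseline and intermediate) as covariates in a regression model using data from subjects that discontinued the treatment".

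**Code.** In SAP 15.5.2 the step 2 statement for week-12 SANDE is "MONOTONE REG(AVAL = TRT AGE SEX / DETAILS". In SAP 15.5.1 the statement for week-4 Schirmer is "MONOTONE REG(AVAL = TRT AGE SEX BASVAL / DETAILS". Each line is the same in the standard column (retrieved-dropout donors) and the alternative column (vehicle donors).

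**Status.** The revision history for SAP version 2.0 records "SAS code for primary analysis in appendix". Section 7.9 opens with "The following changes have been included, compared to the protocol [1", and its list does not include this difference. Neither document says whether text or code prevails.

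**The concern.** A programmer who runs the appendix as printed obtains an analysis that differs from section 10.1.2 on both co-primary endpoints. For SANDE the difference is substantial in kind: a patient missing at week 12 is imputed from arm, age class and sex alone, even when the week-8 score is known. The analysis model then adjusts for a baseline score that played no part in the imputation. That adds noise and discards what the patient's own scores show.

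A second consequence is the choice of method. The SAP falls back from retrieved-dropout imputation (MI-RD) to Copy Reference when there are too few retrieved dropouts for the regression, and decides this at the time of analysis. The coded regression is smaller, so it may be estimable where the text model is not.

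Key secondary endpoints 1 to 3 (SAP 10.2.2.1 to 10.2.2.3) and the tipping-point analysis (10.1.3) reuse the same method.

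**Working it through.** **1. The plan's own figures (SAP section 5).** With 45 per arm and one-sided 0.025:
- SANDE: noncentrality 15 / (20 × √(2/45)) = 3.56 on 88 degrees of freedom gives 94.04% (stated 94.0%).
- Schirmer: 35% against 5%, pooled normal approximation, gives 95.76% (stated 95.8%).
- The product is 90.06% (stated 90%).

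These reproduce. The point does not depend on them.

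**2. Step 2 predictors side by side.**

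| Endpoint | SAP text and protocol | Code, both columns | Missing from code |
|---|---|---|---|
| SANDE week 12 | arm, age class, sex, baseline, weeks 2, 4, 8 | arm, age class, sex | baseline, weeks 2, 4, 8 |
| Schirmer week 4 | arm, age class, sex, baseline, week 2 | arm, age class, sex, baseline | week 2 |

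The omitted scores stand in the VAR list but not among the effects written for AVAL. Reading the previous step as the coded step 1 does not remove the conflict, because that step contains those scores. Coded step 1 in turn leaves out gender and age class, which the text includes.

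**3. Coefficients (two-level age class and sex).**
- SANDE: code 1 + 3 = 4; text 4 + 4 = 8.
- Schirmer: code 1 + 4 = 5; text 5 + 1 = 6.

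One residual degree of freedom therefore needs at least 5 against 9 retrieved dropouts for SANDE, and 6 against 7 for Schirmer. These minima are necessary, not sufficient. With an assumed 30/70 sex split, the coded SANDE model was rank-deficient in about 39% of draws with 5 donors, 24% with 6 and 8% with 8.

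**4. Effect on the SANDE estimate.** Assumptions not in the documents: equal correlation ρ between visits (0.3 or 0.6), random dropout, vehicle donors, 10% missing per arm, and an effect reached in quarter steps (3.75, 7.5, 11.25 and 15 at weeks 2, 4, 8 and 12). Among vehicle donors each of the four earlier scores has slope ρ/(1 + 3ρ), that is 0.158 or 0.214. The part of the effect kept in a missing cenegermin patient is:
- Code: 0, so the estimate is 15 − 0.1 × 15 = 13.50.
- Text, ρ = 0.3: 0.158 × 22.5 = 3.55, so 15 − 0.1 × 11.45 = 13.86.
- Text, ρ = 0.6: 0.214 × 22.5 = 4.82, so 15 − 0.1 × 10.18 = 13.98.

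The gap is 0.36 to 0.48 points when only week 12 is missing. If week 8 is missing too and also drawn from vehicle, the slopes are ρ/(1 + 2ρ) on a sum of 11.25, and the gap is 0.21 to 0.31.

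**5. Effect on SANDE power.** Simulation on the same assumptions, week 12 only missing: 50 per arm, 5 missing in each, SD of change 20, AVAL as the score, ANCOVA on arm, baseline, age class and sex, Rubin pooling. Ranges run over the two correlations.

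| True effect | Code | Text | Code lower by |
|---|---|---|---|
| 15 points | 93.0–97.5% | 97.2–98.5% | about 1–4 points |
| 10 points | 60–73% | 70–76% | about 3–10 points |

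The 1-point end is about the size of simulation error.

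**6. Schirmer.** With 35% against 5% responders, vehicle donors and random dropout, the difference is 0.2 to 0.4 percentage points smaller. Power is 96.6–98.1% against 96.9–98.3%.

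**The case against.** The best defence is that this is a clerical slip with an obvious resolution. The protocol, both subsections of SAP 10.1.2 and the missing-at-random analysis in 10.1.3 all name baseline and intermediate values. The appendix looks like a template: it has a placeholder for the age cut-off and uses two different names for the sex variable. The SAP introduction calls the plan general guidelines and sends deviations to the study report. In the planned case the printed code shrinks the effect, so the error is conservative, and power stays close to the 94.0% planned.

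Most of that stands, and it limits what can be claimed. A reader might infer that the plan offers two equally valid primary analyses; the agreement of the other sections does not support that. A reader might also say that SANDE AVAL is undefined between score and change. The heading of 15.5.2 does name the change, but step 1 imputes the score and AVAL shares a variable list with the visit scores, so the score is the better-supported reading. Finally, a reader might infer inflated type I error. That needs cenegermin patients doing badly and vehicle patients doing well to be the ones missing, and nothing in the documents suggests such a pattern.

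What does not stand is leaving the code as it is. It is headed as the primary analysis code, is not called illustrative, and would give a weaker analysis if run.

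**Conclusion.** The point holds as a mismatch between code and text. The step 2 code for both co-primary endpoints does not implement the SAP text or the protocol, and the code is what should change. The mismatch and the coefficient counts need no assumption beyond two-level factors.

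The sizes are illustrative, since the documents give no dropout mechanism, between-visit correlation or expected number of retrieved dropouts. On the assumptions above, the SANDE effect is about 0.2 to 0.5 points smaller. The power loss is small at the planned 15 points and becomes material if the true effect is nearer 10. For Schirmer it is negligible.

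The code can also alter whether MI-RD or Copy Reference is used for SANDE. It would be too strong to say that any given number of retrieved dropouts forces one method: the counts are only lower bounds, and the SAP leaves the decision to the time of analysis. The sensitivity and supportive analyses show dependence on the imputation but do not correct the primary one.

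**What to change.** Before unblinding:

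- Change step 2 for SANDE to `AVAL = TRT AGE SEX BASVAL SANDE_W2 SANDE_W4 SANDE_W8` and for Schirmer to `AVAL = TRT AGE SEX BASVAL SCHIRMER_W2`. Drop `TRT` in the vehicle-donor column, where it is constant among donors.
- Add age class and gender to step 1, as the text says.
- State that section 10.1.2 governs over the appendix code, and that SANDE AVAL is the week-12 score.
- Make the choice between MI-RD and Copy Reference blind, at the Blind Data Review Meeting (SAP 7.10), on whether the text model is estimable. The documents give no basis for a fixed minimum number of retrieved dropouts, so none is proposed.

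The cost is a few lines of code and a short SAP amendment, with no new data. The downside is that the larger SANDE model needs more retrieved dropouts, so Copy Reference becomes more likely. On the assumptions above, Copy Reference with the text model brings a true 15-point effect down to about 14 by design.

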4.7 Eligible eye

Assuming that all the inclusion/exclusion criteria are met in both eyes, the worse eye (eligible eye) will be determined at the baseline visit using a stepladder approach, as follows:

1. Schirmer’s Test: worse eye determined as eye with lower Schirmer I score.
2. NEI score: if Schirmer I score is the same in both eyes, worse eye will be determined by NEI score (cornea + conjunctival staining).

If all the above are identical, determination of the worse eye will be based on the investigator’s judgement, otherwise the right eye will be used as the eligible eye.

5. Sample size justification

The sample size of the study is calculated based on results from previous studies.

Sample size was calculated according to the following assumptions:

- randomization ratio 1:1.
- a difference of 30% in Schirmer I rate of responders (value >10mm/5min at week 4.) in favor of rhNGF treatment at Week 4, with a responder rate of 5% for vehicle.
- 15 points in Global SANDE score improvement at Week 12, with a standard deviation of 20 points.

Based on these assumptions, a total sample size of 90 evaluable patients (100 pts considering 10% of patients not evaluable after enrollment) allows to achieve an overall power of 90% to show superiority of rhNGF eye drops solution vs vehicle in terms of both co-primary endpoints, considering a one-sided alpha of 0.025. Specifically:

- A power of 95.8% is achieved for Schirmer I primary endpoint.
- A power of 94.0% is achieved for SANDE primary endpoint.

6. Randomization and blinding

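### Patients who finish the 4-week course but miss week 12 SANDE are imputed from patients who stopped treatment; if MI-RD is used, the bias can favour either arm and its size is unknown

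*SAP*

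**What the plan says.** The estimand for both co-primaries is treatment policy in the FAS (SAP 7.3). Treatment ends at week 4 (SAP 4.4) and the SANDE co-primary is the change at week 12.

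The protocol (9.4.3.1) states openly that missing data are assumed to resemble those of retrieved drop-outs, and defines the donors: "Retrieved drop-out patients are defined as patients who discontinue study treatment and decide to remain in the study". SAP 10.1.2 repeats the definition. For SANDE, SAP 10.1.2.2 first fills intermittent gaps under MAR. For all remaining monotone-missing values, "only non-missing values from retrieve dropouts will be used to inform the regression model". Its text lists baseline SANDE, gender, age class and the intermediate SANDE scores as explanatory variables.

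The standard code in SAP 15.5.2 restricts the model to "MNAR MODEL(AVAL / MODELOBS= (EOTSTT='NOT COMPLETED" and regresses week 12 SANDE on treatment, age and sex only. The SAP does not define EOTSTT; it is read here as end-of-treatment status.

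If there are too few retrieved drop-outs for the model to converge, the plan moves to Copy Reference, whose code fits the model on vehicle patients. MI under MAR with same-arm donors (SAP 10.1.3), a tipping-point analysis (SAP 10.1.3) and complete cases (SAP 10.1.4) are planned around the primary analysis.

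**The concern.** A patient who takes the full course and is lost between weeks 4 and 12 has had no treatment-discontinuation event. Under treatment policy, that patient's unseen value is one that follows complete treatment. The donors are patients who stopped early. The protocol gives grounds for expecting the two groups to differ: patients may be discontinued for poor response, tolerability or worsening (3.3.1, 6.3.1), and the sponsor reports that the phase II TID benefit on SANDE was at its best at week 12, after a 4-week course (2.2).

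Nothing else in the primary imputation corrects this. Week 12 is the last variable in the MCMC list and week 16 is not used, so the MAR step never fills a missing week 12 value. The coded regression omits baseline and the week 2, 4 and 8 scores, so a completer's own course after treatment cannot pull the imputed value towards what that patient was experiencing. At stake are the accuracy of the estimate for a co-primary endpoint and, in unfavourable configurations, its type I error.

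**Working it through.** **The plan's own figures.** Inputs from SAP section 5: "15 points in Global SANDE score improvement at Week 12, with a standard deviation of 20 points"; "a difference of 30% in Schirmer I rate of responders", "with a responder rate of 5% for vehicle"; "randomization ratio 1:1"; "considering a one-sided alpha of 0.025"; 90 evaluable, so 45 per arm.

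- SANDE: standard error 20 × √(2/45) = 4.2. Two-sample noncentral t power is 94.0%, as stated.
- Schirmer: 5% against 35%, normal approximation with pooled variance, 95.8%, as stated.
- Both: 0.9576 × 0.9404 = 0.9006, matching the stated 90%. Enrolment: 90/0.90 = 100.

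The sample size is not at issue.

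**Bias if MI-RD is used.** Count reduction in SANDE as benefit. In each arm let m be the share that completed treatment but misses week 12, and g the mean reduction in donors minus that in completers (negative if early stoppers do worse). Imputing a share m at the donor mean moves the arm mean by m × g. Treatment is in the model, so each arm has its own g:

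bias = mT·gT − mV·gV, positive when it favours cenegermin.

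All values of m and g below are assumed. The 10% in SAP section 5 is the share not evaluable after enrolment, not the share of completers without week 12 SANDE.

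| mT / mV | gT / gV | Bias (points) | % of 15 |
|---|---|---|---|
| 10% / 10% | −15 / 0 | 0.10 × (−15) − 0 = −1.5 | −10% |
| 10% / 10% | 0 / −15 | 0 − 0.10 × (−15) = +1.5 | +10% |
| 10% / 10% | −15 / −15 | −1.5 + 1.5 = 0 | 0 |
| 5% / 15% | −15 / −15 | −0.75 + 2.25 = +1.5 | +10% |
| 15% / 5% | −15 / −15 | −2.25 + 0.75 = −1.5 | −10% |
| 20% / 20% | −15 / 0 | −3.0 | −20% |
| 20% / 20% | 0 / −15 | +3.0 | +20% |

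Against the standard error of 4.2, 1.5 points is 1.5/4.2 = 0.36 standard errors and 3 points is 0.71.

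**Simulation.** 1,500 replicates of proper multiple imputation with Rubin's rules; 50 per arm, SD 20, 8 retrieved drop-outs per arm, and a week 8 score correlated 0.6 with week 12. The donor model used treatment and age class.

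- Five completers missing per arm: bias −1.6 when only cenegermin stoppers are 15 points worse, +1.6 when only vehicle stoppers are. Using treatment completers as donors, with the week 8 score in the model, the bias is about 0.1.
- No true effect, both arms' stoppers 15 worse, 2 cenegermin and 8 vehicle completers missing: bias +1.6 (formula: 0.04 × (−15) − 0.16 × (−15) = +1.8). One-sided rejection is 4.1%, against 2.3% with completer donors.
- No gap in either arm, 15-point effect: power 90.4% with retrieved-drop-out donors and 94.5% with completer donors. Part of this difference comes from using the week 8 score.

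**Copy Reference instead.** Vehicle patients are imputed from vehicle patients generally, so vehicle early stoppers no longer stand in for vehicle completers. Cenegermin completers are imputed from vehicle patients. If their true benefit is 15 points and 10% are missing, the effect moves by 0.10 × (−15) = −1.5 points.

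**The case against.** The strongest reply is that this is a declared assumption whose robustness is already examined. The MAR sensitivity analysis draws on the patient's own arm and uses baseline and intermediate values, which is close to what completers need, and complete cases are also run. This stands in part: a mismatch could be seen. But neither analysis changes the primary test, and the tipping point shifts only imputed cenegermin values without separating completers from discontinuers.

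Second, a reader might infer that many imputations will rest on two or three donors and that vehicle early stoppers will inflate the effect. The documents do not support both together. If, say, 5% of 100 patients stop treatment and half remain, there are 100 × 0.05 × 0.5 = 2.5 donors; a model with an intercept, treatment, age class and sex has four parameters and cannot be estimated from them. The plan provides Copy Reference for that case, and that inflation then does not arise. The simulation needed 8 donors per arm, 16% of each arm, to keep MI-RD in use. Even so, SAP 10.1.2.1 motivates Copy Reference by what happens after discontinuation, so its use for cenegermin completers is still a mismatch, though usually a conservative one.

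Third, loss after week 4 may itself be informative, so imputing completers under MAR is not neutral. This stands and shapes the fix.

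**Conclusion.** The mismatch is real in both the SAP text and the code: on the MI-RD path, treatment completers without week 12 SANDE are given values modelled only on treatment discontinuers. The protocol's rationale does not reach them.

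The size is unknown. It is about ±1.5 points at 10% and ±3 points at 20% completer missingness for an assumed 15-point gap in one arm, and nil when gap and missingness match across arms. If few completers are lost it will be small. A reader might infer that the rule systematically favours cenegermin, or that it is reliably conservative. Neither follows: under MI-RD the sign depends on both arms, and under Copy Reference the pull is usually towards zero. The 4.1% rejection rate belongs to one chosen configuration and is not a forecast for this trial.

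The change should be made because it aligns the donors with the stated estimand at little cost. The point does not put the sample size or the trial's validity in doubt.

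**What to change.** Before unblinding, split step 2 of SAP 10.1.2.2 and its code by treatment status:

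- Patients who completed the 4 weeks and miss week 12: impute from same-arm treatment completers with week 12 observed, using baseline and intermediate SANDE with age class and sex.
- Patients who discontinued treatment: keep retrieved-drop-out donors, with Copy Reference as the fallback, for this group only.
- Define EOTSTT in the SAP.
- Keep the present rule for all missing values, and the tipping point, as sensitivity analyses.

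The cost is SAP wording and one extra PROC MI call. The downside is a less conservative imputation for cenegermin completers, whose loss after week 4 may be informative; the retained sensitivity analyses cover that. SANDE severity and frequency at week 12 are analysed by reference to the same section and would follow; the same step 2 wording for IDEEL, NEI and TFBUT should be checked at post-treatment visits.
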